11.7 Case Report Form

All patient data generated during the study will be recorded on the eCRF.

The Investigator will ensure that all data are entered promptly, legibly, completely, accurately and conform to source documents, in accordance with specific instructions accompanying the eCRFs, designed specifically for this study and supplied by the representatives of the sponsor for each patient.

The representatives of the sponsor will only consider the eCRFs to be complete after they are reviewed and signed by the Investigator, indicating his/her assurance of the accuracy of all recorded data. It is expected that the Investigator and staff will cooperate with the monitoring team and provide missing data in a timely manner.

11.8 Verification Procedures

In fulfillment of their obligations to the sponsor and to verify compliance with this protocol, ICH GCP guidance, and FDA GCP regulations, the Investigator will permit the representatives of the sponsor, the IRBs/IECs/RECs, the monitor, and regulatory authorities to have direct access to the patient's medical records.

It is the Investigator's obligation to ensure documentation of all relevant data in the patient's medical record, eCRFs, and on study forms, when applicable, according to procedures provided in the protocol and/or supplemental instructions.

The Investigator will maintain a Patient Identification Code List to enable unambiguous identification of the patients (patient names and corresponding subject codes). The Patient Identification Code List is an essential document and as such must be maintained according to the ICH GCP guidelines.

11.9 Retention of Records

All documentation pertaining to the study will be retained by the sponsor in accordance with US FDA regulations and the ICH GCP guidance document.

The representatives of the sponsor will provide each Investigator with a study file, which will be used to file the Investigator's Brochure, protocol, drug accountability records, correspondence with the IRB/IEC and the sponsor, and other study-related documents.

The Investigator agrees to keep records and those documents that include (but are not limited to) the identification of all participating patients, medical records, study-specific source documents, source worksheets, all original signed and dated ICFs, copies of all eCRFs, query responses, and detailed records of drug disposition, to enable evaluations or audits from regulatory authorities and the sponsor or its designees.

The Investigator will retain records required to be maintained under federal regulations for a period of 2 years following the date a marketing application is approved for the drug for the indication for which it is being investigated; or, if no application is to be filed or if the application is not approved for such indication, until 2 years after the investigation is discontinued and FDA is notified. However, these documents will be retained for a longer period if required by the applicable regulatory requirement(s) or if needed by the sponsor. In addition, the Investigator must make provision for the patient's medical records to be kept for the same period of time.

Patients' medical records and other original data will be archived in accordance with applicable regulations and requirements established by the investigational sites.

11.10 Insurance and Indemnity

The sponsor's obligations regarding insurance and indemnification are described in other documents or agreements.

11.11 Audit and Inspection

The Investigator must permit study-related quality oversight monitoring, quality assurance audits, IRB/IEC/REC review, and regulatory agency inspections and provide direct access to source data documents. It is important that the Investigator(s) and their relevant personnel are available during the monitoring, audit, or inspection visits and that sufficient time is devoted to the process.

It is the responsibility of KRI to perform sponsor quality oversight, as part of the quality assurance and quality control programs. The purpose of a quality assurance audit, which is independent of and separate from routine monitoring or quality control functions, is to evaluate trial conduct and compliance with the protocol, the principles of ICH GCP, and other applicable regulatory requirements.

12.0 USE OF INFORMATION

12.1 General Aspects

All information concerning KRI, such as patent applications, formula, manufacturing processes, basic scientific data or formulation information supplied by KRI and not previously published, are considered confidential and will remain the sole property of KRI. The Investigator agrees to use this information only in accomplishing this study and will not use it for other purposes without the written consent of KRI, except for official representatives, such as regulatory authorities.

It is understood by the Investigator that the information developed in this clinical study, in connection with the development of K-161 will be used by KRI and, therefore, may be disclosed by KRI as required to other clinical Investigators, other pharmaceutical companies and to other government agencies. In order to allow for the use of the information derived from clinical studies, it is understood that there is an obligation to provide to KRI complete test results and all data compiled in this study.

12.2 Patient Confidentiality and Data Protection

KRI and its designees affirm and uphold the principle of the patient's right to protection against invasion of privacy. Throughout this study, all data will be linked to the eCRF via a unique identification number and the patient's initials. The data will be masked correspondingly in all data analyses.

However, in compliance with the guidelines and regulations of the US FDA concerning the acceptance of clinical studies in support of IND applications and the ICH GCP (whether performed in the US or elsewhere), and in fulfillment of its obligations to KRI to verify compliance with this protocol, KRI's designee requires that the Investigator to permit its monitor, representatives from the FDA, KRI's designated auditors, IRBs/IECs, and other governmental regulatory authorities to review the patient's primary medical records (source data or documents) including, but not limited to laboratory test result reports, electrocardiogram reports, admission and discharge summaries for hospital admissions occurring during a patient's study participation, and autopsy reports related to deaths occurring during the study.

Should access to such medical records require a waiver or authorization separate from the statement of informed consent, the Investigator will obtain such permission in writing from the patient before the patient is entered into the study.

12.3 Final Report and Publication Policy

All information regarding this study will be kept strictly confidential. All data derived from the study will be the property of KRI. The Investigator must undertake not to submit any part of the data from this study for publication without prior consent of KRI. KRI may disclose data derived from the study to other Investigators and drug regulatory authorities.

After completion of the study, and as agreed by the Investigator and KRI, the Investigator may send a draft manuscript to KRI to be reviewed in order to reach an agreement regarding publication. The Investigator must receive written approval from KRI before the final version of the manuscript is submitted for publication.

At the conclusion of the study, after the data are analyzed, KRI or its designee will prepare a final clinical report.

Kowa Research Institute, Inc.

K-161-3.01

A Phase 3, Prospective, Double-masked, Randomized, Multi-center, Vehicle-controlled, Parallel-group, 12-week Administration and 40-week Extension Study Confirming the Efficacy and Safety of K-161 Ophthalmic Solution for the Treatment of Moderate to Severe Dry Eye Disease

NCT05403827

2023-10-03

[figure not shown]
[figure not shown]
Addendum to Statistical Analysis Plan

Version 1.0

[figure not shown]
Prepared by:

Signature Page:

Kowa Research Institute, Inc.

Kowa Research Institute, Inc

Introduction:

The objective of this Statistical Analysis Plan (SAP) addendum is to provide modifications and corrections to the final *K-161-3.01* SAP, dated May 24, 2023.

List of Modifications/Corrections to the final *K-161-3.01* SAP Dated May 24, 2023:

1. Change to per protocol set (PPS) defined in SAP Section 4.4.2

PPS is redefined to exclude subjects with major protocol deviations (PDs) related to primary and key secondary endpoints, rather than all major PDs as defined by the PD Guidance Plan. These major PDs were identified during blinded data review. This change is made to have a more meaningful PPS focusing on primary and key secondary endpoints and to avoid exclusion of subjects with deviations that do not impact the primary or key secondary efficacy assessments.

2. Presentation for actual treatment

The definition of actual treatment for subjects who received incorrect treatment different from their randomized treatment was reaffirmed during the data review meeting. In the safety analyses, a subject will be classified as part of the K-161 group in accordance with SAP Sections 4.4.3 and 4.4.5 if they were initially assigned to the placebo group but received at least one kit of the K-161 treatment. For other treatment errors, the actual treatment group will match the randomized treatment unless a subject was initially allocated to the K-161 group but received placebo treatment kits throughout the study. These decisions are based on the understanding that one kit is used for 3 weeks of treatment.

3. Modifying Race classifications

Race (see SAP Section 6.1) will be handled according to CDISC SDTM terminology like below.

Race as collected	CDISC SDTM terminology
White	White
Black or African American	Black or African American
American Indian or Alaska Native	American Indian or Alaska Native
Asian Indian	
Chinese	
Filipino	
Japanese	Asian
Korean	
Vietnamese	
Other Asian	
Native Hawaiian	
Guamanian or Chamorro	Native Hawaiian or Other Pacific Islander
Samoan	
Other Pacific Islander	
Not reported	Not reported
Unknown	Unknown
Other	Other

4. Number of days of rescue medications and artificial tears

When the start date or the stop date is missing entirely, it will be left missing. When the start and stop dates are partially missing, they will be imputed for the prior [REDACTED] usage, as defined in SAP Section 7.3, in the following manner:

For partially missing start dates:

- If the year is provided but the month is missing, the month will be set to January.
- If both the month and year are provided but the day is missing, the day will be set to the first day of the month.

For partially missing stop dates:

- If the year is provided but the month is missing, the month will be set to December.
- If both the month and year are provided but the day is missing, the day will be set to the last day of the month.
- If the imputed date falls later than three days before Visit 1, the day will be set to three days before Visit 1.

The number of days of artificial tear and rescue medication usage, as described in SAP Sections 7.3 and 8.4, will be calculated as the sum of days if a patient has multiple medication records.

The calculation will encompass the entire duration, considering the earliest start date to the latest end date, particularly in cases where there is an overlap between the specified periods.

5. Dose frequency of [REDACTED]

The dose frequency of [REDACTED] collected in the electronic data capture was reviewed during the blinded data review, in accordance with SAP Sections 7.3 and 8.4. The number of doses per day will be calculated based on the following table, which will then be used to determine the total number of doses by multiplying it with the number of days.

Frequency as collected	Corresponding number of doses per day
QH = every hour	16 doses/day (considering 16 hours awake)
Q2H = every 2 hours	8 doses/day (considering 16 hours awake)
Q3H = every 3 hours	5.33 doses/day (considering 16 hours awake)
Q4H = every 4 hours	4 doses/day (considering 16 hours awake)
2 times/week	2 doses/7 days = 0.29 doses/day
3 times/week	3 doses/7 days = 0.43 doses/day
3-4 times/week	3.5 doses/7 days = 0.5 doses/day
3-5 times/week	4 doses/7 days = 0.57 doses/day
5 times/week	5 doses/7 days = 0.71 doses/day
Q2W = every 2 weeks	1 dose/14 days = 0.07 doses/day
Q6M = every 6 months	1 dose/182.625 days = 0.01 doses/day

6. Treatment compliance

Compliance will be considered as missing if the numerator or denominator in SAS Section 7.7.2 is not calculated due to missing data.

7. Statistical approach for primary efficacy endpoints

Originally, two statistical approaches were planned, namely multiple imputation (as outlined in SAP Section 8.1.2) and control-based mean imputation (as described in SAP Section 8.1.4). The former approach was planned to switch the latter one if there were not enough patients to develop imputation models. The decision to use the latter approach for the primary analyses was made based on the results of the data review meeting, which determined the final approach: control-based mean imputation.

8. Typo in the SAS code

From the formula in SAP Section 8.1.4:

$$\hat{V}(\hat{\delta}_{new}[c]) = \left[A_2 + (f_2^{k=1})^2 \right] (\hat{V}_2^{k=1} + \hat{V}_{1,MAR}) + \left[A_2 (\hat{\mu}_2^{k=1} - \hat{\mu}_{1,MAR} - c)^2 \right],$$

the sign is modified from "+" to "-" in the code in SAP Section 8.1.4 as follows:

```
V_delta_new_c= (A2 + (f2_k1)**2)*(V2_k1 + V1_MAR) + (A2*(mu2_k1 - mu1_MAR - c)**2);
```

Final programs have been corrected to reflect this.

9. Range of conservative values (c) for sensitivity analysis in SAP Section 8.1.6

The following ranges of c will be defined to find the tipping point c_t :

- Eye dryness score (visual analog scale): 0 to $(100 - \hat{\mu}_{1,MAR})$,
- Conjunctival sum fluorescein staining score: 0 to $(24 - \hat{\mu}_{1,MAR})$.

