8.3 Permitted Medication and Rescue Therapy

Contact lenses are allowed only during the 40-week Extension Period (except for study visit days before all visit assessments are completed). Contact lenses should be removed prior to the administration of study drug and may be reinserted at least 15 minutes following administration. If a patient is using another prescription eye drop in combination with the study medication, the concomitant use of contact lenses is not recommended for the duration of such combination therapy.

The following medications are permitted as long as the dosage is stable:

- Systemic tetracycline compounds (e.g., tetracycline, doxycycline, or minocycline), macrolides (e.g., azithromycin): for at least 30 days prior to Visit 1 and dose will remain stable until the end of the 12-week Primary Period
- Any medication (topical and systemic) known to cause ocular drying, such as systemic anticholinergic medications (e.g., atropine, homatropine), antidepressants and antipsychotic agents, statins, diuretics, beta-blockers, NSAIDs: for at least 30 days prior to Visit 1 and dose will remain stable until the end of the 12-week Primary Period
 - Episodic use of anticholinergic drops for eye examination and episodic use of systemic NSAIDs are allowed during the study except for within 2 days prior to any study visit.
- Omega-3 fatty acid supplements in doses above 3000 mg/day, oral hormonal contraceptives, hormone replacement therapy for menopause: for 12 weeks prior to Visit 1 and dose will remain stable until the end of the 12-week Primary Period. Omega-3 fatty acid supplements in doses equal to or below 3000 mg/day are permitted.

Any prohibited and restricted medications, devices, and procedures indicated for dry eye disease are permitted as “rescue therapy” after all assessments are completed at Visit 6 (except for study visit days before all visit assessments are completed) (Table 1).

Especially, [REDACTED] will be summarized as described in Section 5.2.10. All other prohibited medications, other than isotretinoin, systemic [REDACTED], and restricted medications, devices, and procedures are permitted as “permitted therapy” after all assessments are completed at Visit 6 (except for study visit days before all visit assessments are completed). If more than one topical ophthalmic medicinal product is being used, the medicinal products must be administered at least 15 minutes apart.

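### Does the SAP Addendum leave the count of days and doses of rescue medication and artificial tears undefined?

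*SAP*

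**What the plan says.** Item 4 of the SAP Addendum deals with days of rescue-medication and artificial-tear use. Partly missing dates are widened for earlier use: "they will be imputed for the prior [REDACTED] usage, as defined in SAP Section 7.3". When there are several records, the number of days "will be calculated as the sum of days if a patient has multiple medication records". The next sentence has the calculation cover the whole duration, "considering the earliest start date to the latest end date, particularly in cases where there is an overlap between the specified periods".

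Item 5 converts each recorded dosing frequency into doses per day, "which will then be used to determine the total number of doses by multiplying it with the number of days". Its last row, for every 6 months, reads "1 dose/182.625 days = 0.01 doses/day".

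Both items refer to SAP Sections 7.3 and 8.4 of the SAP of May 24, 2023. That SAP is not among the supplied documents. On the Protocol side, Section 8.3 says that an item whose name is blacked out "will be summarized as described in Section 5.2.10", and the content of Section 5.2.10 is itself blacked out. Protocol Section 10.7 lists earlier use of a blacked-out product among the demographic and baseline summaries.

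**The concern.** Three things catch the eye.

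- **Two day counts.** A plain sum counts overlapping days twice. A span from earliest start to latest end counts days without use whenever there is a gap. The word *particularly* does not confine the span to overlaps, and gaps are not mentioned. Overlaps are foreseeable, because the date imputation moves starts back to January or the first of the month and stops forward to December or the month's end.
- **An unclear multiplicand.** Item 5 multiplies by the number of days without saying whether this is each record's own days or the patient-level count from item 4. The two differ when a patient's records carry different frequencies.
- **A coarse factor.** The printed every-6-months value is almost double its own fraction.

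At stake is whether two programmers working from the Addendum would produce the same usage tables.

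**Working it through.** **1. The item 5 table.** Inputs are the fractions and rounded values printed in the Addendum. All 11 rows reproduce at two decimals:

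- Every 1, 2, 3 and 4 hours over 16 waking hours: 16, 8, 5.33 and 4.
- Weekly rows: 2/7 = 0.29, 3/7 = 0.43, 3.5/7 = 0.50, 4/7 = 0.57, 5/7 = 0.71.
- Every 2 weeks: 1/14 = 0.07.
- Every 6 months: 1/182.625 = 0.005476, which is 0.01 at two decimals.

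There is no arithmetic error. As a multiplier, the rounded every-6-months value is 0.01/0.005476 − 1 = 82.6% too high. The other ten rows are within 2.0% (the largest is every 2 weeks, 0.07 against 0.0714, −2.0%). In doses:

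| Period | Exact fraction | Printed 0.01 | Excess |
|---|---|---|---|
| 280 days (40 weeks × 7) | 280/182.625 = 1.53 | 2.80 | 1.27 |
| 365 days | 365/182.625 = 2.00 | 3.65 | 1.65 |

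**2. The day count.** The documents give no record-level data, so these records are illustrative. Each record's length is end − start + 1.

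| Records (study days) | Sum of records | Whole-patient span | Merge overlaps, then sum | Distinct days covered |
|---|---|---|---|---|
| 100–109, 200–209 | 20 | 110 | 20 | 20 |
| 100–109, 105–114 | 20 | 15 | 15 | 15 |
| 100–109, 105–114, 300–309 | 30 | 210 | 25 | 25 |

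The two sentences of item 4 fit together in only one way that gives both a job: sum separate periods, and run from earliest start to latest end where periods overlap. That is the fourth column, and it equals the distinct days in every row. If the span applied to every patient with several records, the sum would never be used, although the sum sentence is written for exactly those patients. The 110 and 210 therefore come from a strained reading.

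**3. Total doses.** For the third set at 4 doses/day, the four columns give 30 × 4 = 120, 210 × 4 = 840, 25 × 4 = 100 and 25 × 4 = 100. Setting the strained reading aside leaves 100 against 120.

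With different frequencies (every 4 hours on Days 100–109, twice a week on Days 105–114), working by record gives 10 × 4 + 10 × 2/7 = 42.9. Attaching one frequency to the merged 15 days gives 15 × 4 = 60 or 15 × 2/7 = 4.3. Since each frequency belongs to a record, the per-record calculation is the natural one here.

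**4. Where the counts go.** Protocol Sections 10.4 and 10.4.1 analyse changes from baseline in staining scores, EDS, OSDI, Schirmer's test and TFBUT. For the primary endpoints the covariates are baseline value, sex and treatment, and the secondary endpoints are handled similarly. Days or doses of rescue use do not enter. The intercurrent events in Section 10.2 are treatment discontinuation for an adverse event or for lack of efficacy, not rescue use. Section 8.3 permits dry-eye rescue therapy only after the Visit 6 assessments, so permitted rescue use comes after the Day 85 measurements. The supplied documents show no between-arm test of these counts.

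**The case for a change.** The strongest case for acting is that an addendum written to modify and correct a SAP should not leave a derivation to inference. *Particularly* is not *only*, gaps go unmentioned, the multiplicand in item 5 is unspecified, and a few lines would cure all of it. The every-6-months row sits in a table of frequencies as collected, so it is a category the sponsor chose to handle.

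Part of this stands. The wording is loose, and partly overlapping records of the same product do leave room for 100 or 120 doses in the third example.

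The rest is weaker. The Addendum only modifies a SAP whose relevant sections are not supplied, so it cannot be shown that the rule is missing from the full plan. The exact fraction is printed in the same cell as the rounded value, and nothing shows that programs use the latter. The table is openly approximate elsewhere, with 16 waking hours assumed and 3–4 times a week taken as 3.5.

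Nor is the obvious remedy clean. Counting distinct days for duration while summing doses over each record's own days gives 10 × 4 + 10 × 4 + 10 × 4 = 120 in the third example, against 100 from the 25 distinct days. Removing duplicate records would not clearly help, because partly overlapping records are not plainly duplicates.

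**Conclusion.** No change to the plan is needed. Item 4 is a wording gap that an analyst fills sensibly by merging overlapping records and summing the separate periods, which counts each covered day once. The every-6-months factor is correct rounding shown beside its exact value. It would matter only if the rounded value were used in programs, at about 1.3 extra doses per such record over 280 days; the documents do not say how many records carry that frequency.

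The conclusion rests on three points. The record sets above are illustrative. SAP Sections 7.3 and 8.4 are not supplied and the product names are blacked out, so a clarifying rule or a further use of these counts can be neither confirmed nor excluded. On the text that is available, the effect stops at descriptive usage summaries, and no effect on the primary, key secondary or ordered secondary analyses is shown. If the derivation specifications are revised for another reason, it would do no harm to record the merge rule, the use of unrounded fractions and the handling of partly overlapping records of one product.

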1.0 INTRODUCTION AND RATIONALE FOR DOSE SELECTION

1.1 Background Information

Dry eye disease (DED) is a multifactorial disease of the ocular surface characterized by a loss of homeostasis of the tear film, and accompanied by ocular symptoms, in which tear film instability and hyperosmolarity, ocular surface inflammation and damage, and neurosensory abnormalities play etiological roles ([Nelson 2017](#)). Patients with DED often experience ocular discomfort, visual disturbance, and other ocular symptoms. While the prevalence of DED is difficult to report due to varying definitions and diagnostic criteria, the global prevalence of DED is estimated to be between 5% and 50%, and increases with age ([Bron 2017](#)). In the United States (US), it is estimated that as many as 3.2 million women and 1.7 million men over the age of 50 have DED, with a projected 40% increase in number of patients affected by the year 2030 ([Schaumberg 2002](#), [Schaumberg 2003](#), [Schaumberg 2009](#)).

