4.0 PATIENT ELIGIBILITY AND WITHDRAWAL CRITERIA

4.1 Inclusion Criteria

Patients are eligible for the study if all of the following criteria are met:

1. Be at least 18 years of age at the time of Informed Consent Visit
2. Have a reported history of DED in both eyes [REDACTED]
and a history of eye drop use for dry eye symptoms

11. Be willing and able to read, sign, and date the informed consent and Health Insurance Portability and Accountability Act (HIPAA) documents after the nature of the study is explained and prior to initiation of Visit 1 procedures or exams
12. Have a negative urine pregnancy test, if the patient is a female of childbearing potential and is not either nursing or planning a pregnancy. Women of childbearing potential who are not surgically sterilized [bilateral tubal ligation, hysterectomy, or bilateral oophorectomy] or post-menopausal [12 months after last menses]), must use adequate birth control throughout the study. Adequate birth control is defined as hormonal – oral, implantable, injectable, or transdermal contraceptives; mechanical-spermicide in conjunction with a barrier such as condom or diaphragm; intrauterine device; or surgical sterilization of partner. For non-sexually active females, abstinence may be regarded as an adequate method of birth control
13. Be willing and able to follow instructions and participate in all study assessments and visits

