10.0 STATISTICAL METHODS AND DATA ANALYSIS

10.1 Sample Size Justification

The parameters to be needed for the calculation of sample size were estimated from the previous Phase 2 study (K-161-2.01US). In order to take intercurrent events (ICEs) into account, 4 different patient patterns are considered: (1) patients who were assigned to K-161 [REDACTED] and had an ICE, (2) patients who were assigned to K-161 [REDACTED] and did not have an ICE, (3) patients who were assigned to vehicle and had an ICE, and (4) patients who were assigned to vehicle and did not have an ICE.

Regarding EDS (VAS), a population mean in each pattern is assumed as follows:

Assigned Treatment	Intercurrent Event	
	Not Occurred	Occurred
K-161 [REDACTED]	(1) -10.0	(2) -3.6
Vehicle	(3) -3.6	(4) -3.6

A common variance, 431.2, and a common ICE occurrence rate, 8%, are assumed among the patterns. In order for EDS (VAS) to have at least 90% power when Holm's method is applied, i.e., in order to have 90% probability that EDS (VAS) is statistically significant when an alpha is set to 0.025 (two-sided), 310 patients/arm will be needed.

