10.4 Analysis of Efficacy Parameters

The primary efficacy endpoints are change from baseline to Day 85 in conjunctival sum fluorescein staining score on study eye and EDS (VAS), which are used regardless of whether or not the following ICEs occur: discontinuation of the study treatment due to an AE or lack of efficacy. Patients' measurements will be made even after occurrence of those ICEs. For each of the primary endpoints, the analysis of covariance with baseline value, sex and treatment as covariates is used in order to make a comparison between the treatment groups. Least squares means will be calculated for the comparison.

The data set to be used for the primary analyses is the FAS.

Missing values will be imputed using the pattern mixture model (PMM) with multiple imputation (MI). Patterns to be used for the PMM are, as feasible, determined in each treatment group by whether or not patients had an ICE, or the type of ICEs if patients had an ICE. For example, if patients who discontinued the study treatment due to an AE had missing values, their missing values will be imputed from the patients who had the same ICE, i.e., discontinuation of the study treatment due to an AE. If enough patients to develop an imputation model in each pattern do not exist, the control-based mean imputation proposed by Mehrotra ([Mehrotra 2017](#)) will be applied instead of the PMM with MI.

If the MI is applied, multiple parameter estimates will be combined using Rubin's rule ([Rubin 1987](#)).

With regard to multiplicity caused by the 2 primary endpoints, Holm's method ([Holm 1979](#)) will be utilized. First, an endpoint with a smaller p-value will be tested at alpha=0.025 (two-sided). If the first test is significant, another endpoint will be tested at alpha=0.05 (two-sided). Otherwise, the second test will not be performed.

Planned analyses at Day 85 including the primary analyses will be performed by unmasked team not involved in the conduct of the study once all patient data until Day 85 are obtained in a fashion to protect the masking of the patients who will be followed in extension. Masked team will have access only to a summary of the results comparing the two arms so the same study team can continue to be masked while conducting the remaining part of the trial until the end of the 52-week Overall Period. The investigational sites will not be unmasked and will not have access to the summary of the results comparing the two arms.

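### Does the variance formula in SAP Addendum item 8 need a covariance term between the two arm means?

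*SAP*

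**What the plan says.** Protocol Section 10.4 describes the comparison for each primary endpoint: "the analysis of covariance with baseline value, sex and treatment as covariates is used". It adds: "Least squares means will be calculated for the comparison". It does not say how sex is weighted in those means.

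SAP Addendum item 7 reports that the data review meeting "determined the final approach: control-based mean imputation". Item 8 then corrects one sign in the SAS line for that estimator's variance and reprints the formula from SAP Section 8.1.4: "V}(\hat{\delta}_{new}[c]) = \left[A_2 + (f_2^{k=1})^2 \right] (\hat{V}_2^{k=1} + \hat{V}_{1,MAR". The formula and the corrected code both use V2_k1 + V1_MAR where the variance of mu2_k1 − mu1_MAR belongs. Because the expression contains c, it also serves the sensitivity analysis in item 9: "The following ranges of c will be defined to find the tipping point".

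The SAP document supplied is the addendum alone. Section 8.1.4 of the SAP of May 24, 2023, from which item 8 takes these quantities, is not in it.

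**The concern.** The variance of a difference equals the sum of the two variances only when the two estimates are uncorrelated. Least squares means from one ANCOVA share the estimated sex coefficient. If the sexes are weighted equally while the sample is mostly of one sex, both means carry the same extrapolation error. That error cancels in the difference, but the sum of variances counts it twice.

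This would matter because the line gives the standard error for both primary endpoints. An overstated standard error makes the test run below its nominal level, costs power, and brings the tipping point forward. The ANCOVA in Protocol Section 10.4 is also the only comparison model in the documents at hand, so a reader would naturally assume that it supplies both means.

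**Working it through.** **Inputs.** From Protocol Section 10.1: "A common variance, 431.2, and a common ICE occurrence rate, 8%, are assumed among the patterns"; EDS mean changes of −10.0 (K-161 without an intercurrent event) and −3.6 (all other patterns); 310 per arm; two-sided alpha 0.025 (z = 2.2414). Three inputs are assumptions:

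- Every patient with an intercurrent event is missing at Day 85, so f = 0.92.
- A2 = f(1 − f)/310, since A2 is not defined in the supplied text.
- The share of women, p. The trial's sex split is not given. The only related figure is the background estimate "3.2 million women and 1.7 million men over the age of 50 have DED", which is 3.2/4.9 = 65%. It describes US patients over 50, whereas the trial's entry criterion is "Be at least 18 years of age at the time of Informed Consent Visit".

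**The plan's own figure.** The diluted difference is 0.92 × 6.4 = 5.888. Then n = 2 × 431.2 × (2.2414 + 1.2816)² / 5.888² = 308.7, or 309 per arm. Adding the mixture variance in the K-161 arm (0.92 × 0.08 × 6.4² = 3.01) gives 309.8, or 310. The stated sample size reproduces.

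**Covariance under the suspected condition.** With one fit, equal sex weights, n observed per arm and N = 2n, each mean has variance σ²[1/n + (0.5 − p)²/(N p(1 − p))]. The second part is common to both arms, so it is their covariance. The printed sum V2 + V1 therefore exceeds the true variance of the difference by the factor 1 + (0.5 − p)²/(2p(1 − p)). This factor is 1 at p = 0.50, 1.049 at 0.65 and 1.167 at 0.75.

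**Item 8 at c = 0.** n = 0.92 × 310 = 285.2, so without the shared part V2 + V1 = 2 × 431.2/285.2 = 3.024. A2 = 0.92 × 0.08/310 = 0.000237. The variance is (0.000237 + 0.8464) × 3.024 + 0.000237 × 6.4² = 2.570, so the correct SE is 1.603. Power is Φ((5.888 − 2.2414 × reported SE)/1.603), because only the reported SE is inflated and not the estimator's spread.

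| Women (assumed) | Covariance | SE as printed | Excess | Power | Actual level of the 2.5% test |
|---|---|---|---|---|---|
| 50% | 0 | 1.603 | 0% | 92.4% | 2.5% |
| 60% | 0.031 | 1.620 | 1.0% | 92.0% | 2.4% |
| 65% | 0.075 | 1.642 | 2.4% | 91.6% | 2.2% |
| 70% | 0.144 | 1.677 | 4.6% | 90.8% | 1.9% |
| 75% | 0.252 | 1.731 | 8.0% | 89.5% | 1.5% |

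**The other ways to obtain the two means.** Simulation used 310 per arm, 8% missing at random and 20,000 runs per scenario, at 65% and 75% women. The null rejection rates of the printed formula at nominal 2.5% were:

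- one fit, equal sex weights: 2.2% and 1.6% (2.5% and 2.5% with the covariance subtracted);
- one fit, observed sex proportions: 2.6% and 2.5%;
- separate fits by arm: 2.6% and 2.3%.

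The printed form is sound in the last two cases. Pairing separate-fit means with the single ANCOVA's variance of the difference gave 3.5% and 5.0%, so that particular substitution would do harm.

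**The case for a change.** The best argument for a change is that the general formula, V2 + V1 minus twice the covariance from whichever fit produced the means, is right in every case and costs one line of code. Item 8 was issued to repair this very line, yet it names neither the model nor the weighting, so the standard error cannot be checked from the addendum alone.

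The algebra stands, and so does the remark that a reader of the addendum alone cannot tell which case applies. The rest is weaker. The addendum lists corrections to a full SAP, and an erratum for one sign need not restate the model behind it. Section 10.4 names the ANCOVA for the comparison but does not say that it yields mu2_k1 and mu1_MAR. The notation gives one a pattern index and the other a MAR label, which fits separate estimation, though it does not prove it. With separate fits the extra term is zero; with observed-proportion weights it is close to zero. In the one remaining case, the change would swap a conservative variance for a smaller one after the data review meeting, when item 8 says the final programs are already corrected.

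The tipping-point argument adds little that can be measured. At a 50:50 split, under the assumptions above, the EDS tipping point is about c = 26.6 with 8% missing and 43.6 with 5% missing. The unknown missing rate therefore dominates any effect of the covariance. Protocol Sections 4.3 and 10.4 keep patients in follow-up after stopping treatment, so 8% missing is itself only an assumption.

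**Conclusion.** No error in the plan is shown, and no change follows. The printed variance falls short only if three things hold together: both means come from one ANCOVA, the sexes are weighted equally, and the sex split is well away from 50:50. The documents establish none of them, and the section that would settle the first two was not supplied. The model behind these two means is a detail to read in SAP Section 8.1.4, not a defect in item 8.

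If all three did hold, the consequence would be modest and on the safe side. At an assumed 65% women, the only share that can be derived from the documents, the EDS standard error would be 2.4% too large and power would be 91.6%, still above the 90% target. At an assumed 75% the figures are 8.0% and 89.5%, half a point below target. The actual level would fall below 2.5%, so a false positive finding would not become more likely. The SE excess hardly depends on the missing rate: with almost no missing data it is still 8.0% at 75% women. The power figures rest on the planning values in Protocol Section 10.1 and on f = 0.92.
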